e. *Exclusion criteria.* 1) People less than 18 years or older than 60 years of age; 2) People with significant cardiac, pulmonary or renal disease, people with diabetes, HIV or Hepatitis B or C; 3) People unable to read and understand English; 4) People unable to provide informed consent; 5) People unwilling or unable to avoid prescription medications, over the counter drugs, dietary supplements and food that are known to alter CYP3A4 expression or activity; people not willing to maintain the recommended diet of consistent calcium and Vitamin D levels during the study or not willing to maintain a daily diary of their food consumption; 6) Women who are pregnant or lactating and women participants of childbearing age not willing to utilize a barrier method of birth control (sterilization will be acceptable); 7) People with allergies to rifampin, clarithromycin or grapefruit juice, people with a corrected QTc interval of $>$ 430 ms in men or $>$ 450 ms in women on electrocardiogram.

General study procedures. This will be a 35-day study, divided into three periods: Baseline, d1-d7; Comparator, d8-d21; Washout, d22-35. The participants will be asked to eat a diet that maintains a consistent amount of vitamin D and calcium for the entire 35 days of the study and will record their daily food intake in a digital diary. They will be given a list of medications and foods to avoid during the study, because they are known to modify CYP3A4 activity.

Baseline Period. Participants will return to the University of Washington Laboratory Services on days 1, 4 and 7 between 8 am - 12 noon for a blood draw. On day 1, they will receive a specimen container for 24-hour urine collection. Urine collection will start on day 6 and continue for 24 hours. Participants will return this completed urine specimen when they return to University of Washington Medical Center on day 7 for blood collection.

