Comparator Period. On day 8, the participants will enter the comparator period of the study. Depending on which of 6 groups group to which they were randomized, the participants will take either (1) 200 mL of water at 8 am for 14 days; (2) rifampin 600 mg with 200 mL of water at 8 pm for 14 days; (3) 200 mL of grapefruit juice at 8 am for 14 days; (4) 200 mL of grapefruit juice at 8 am plus rifampin 600 mg at 8 pm, both for 14 days; 5) clarithromycin 250 mg twice a day at 8 am and 8 pm for 14 days and 6) clarithromycin 250 mg twice a day at 8 am plus rifampin 600 mg with 200 mL of water at 8 pm, both for 14 days.

The grapefruit juice utilized in this study will be obtained from the Florida State Department of Citrus because they have a history of providing a high quality product that has been standardized for CYP3A4 inhibition for studies such as this one. Rifampin and clarithromycin will be dispensed by prescription from the University of Washington Investigation Drug Services.

Participants will return to University of Washington Laboratory Services on days 8, 9, 12, 15, 18 and 21 of the study for a blood draw between 8 am - 12 noon. On day 8, the participants will receive a specimen container for the second 24 hour urine collection. Participants will begin this urine collection on day 20 and return this specimen on day 21 when they return to University of Washington Medical Center. The 24 hour urine collection will need to be refrigerated during the collection period.

Washout Period. During the washout period of 14 days the participants will maintain a consistent diet of Vitamin D and calcium intake. On days 23, 25, 28, 31 and 35, the participants will return to University of Washington Laboratory Services for a blood draw between 8 am - 12

noon. On day 23, the participants will receive a specimen container for the second 24 hour urine collection. Participants will begin this urine collection on day 34 and return this specimen on day 35 when they return to University of Washington Medical Center. The 24 hour urine collection will need to be refrigerated during the collection period. The study will conclude with the return of the 24-hr urine specimen and the d35 blood draw.

C. ANALYTICAL METHODS

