The primary study outcome measures – serum PTH and osteocalcin, plasma calcium concentration and 24-hr urinary calcium and phosphate concentration (normalized for creatinine concentration) – will be measured by the UWMC Department of Laboratory Medicine using established clinical procedures. The concentration of vitamin D₃ species in plasma will be measured in our research lab HPLC-Mass Spectrometry, using published methods developed by our research team.

D. STATISTICAL ANALYSIS PLAN

We will summarize demographic characteristics by treatment group using mean (SD) for continuous variables and frequency (percent) for categorical variables. We define the baseline value of each analyte to be the average of the three pre-randomization measurements, and the post-treatment value to be the analyte measurement after 14 days of treatment. We will use a linear mixed model with random intercepts and main effects for treatment group, the indicator of time (pre- vs. post-treatment), and the interaction of the two. From this model, we will extract the pre-treatment and post-treatment means, the change in analyte comparing pre- vs post-treatment for each group, and the difference in change in analyte comparing each active treatment group with the change observed in the water group. We will use a Wald test to test each difference in change compared with water, and a global Wald test to test the null hypothesis that all pre- vs post-treatment changes were the same across treatment group.

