Effect of Modulating CYP3A4 Activity on Mineral Homeostasis
NCT02019875
06/16/2016

We summarized demographic characteristics by treatment group using mean (SD) for continuous variables and frequency (percent) for categorical variables. We defined the baseline value of each analyte to be the average of the three pre-randomization measurements, and the post-treatment value to be the analyte measurement after 14 days of treatment. We then used a linear mixed model with random intercepts and main effects for treatment group, the indicator of time (pre- vs. post-treatment), and the interaction of the two. From this model, we extracted the pre-treatment and post-treatment means, the change in analyte comparing pre- vs post-treatment for each group, and the difference in change in analyte comparing each active treatment group with the change observed in the water group. We used a Wald test to test each difference in change compared with water, and a global Wald test to test the null hypothesis that all pre- vs post-treatment changes were the same across treatment group.

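### Does the plan need an analysis of the 14-day washout samples, which no named comparison uses?

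*Protocol*

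**What the plan says.** Study Design (Protocol, section B) sets out three periods: 7 days of baseline, 14 of comparator and 14 of washout. In the last of these, diet control continues: "During the washout period of 14 days the participants will maintain a consistent diet of Vitamin D and calcium intake". Blood is drawn on Days 23, 25, 28, 31 and 35. There is also a final urine collection: "Participants will begin this urine collection on day 34 and return this specimen on day 35". No treatment follows.

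Analytical Methods (section C) lists five primary outcomes: serum PTH, serum osteocalcin, plasma calcium, and "24-hr urinary calcium and phosphate concentration (normalized for creatinine concentration". It attaches no visit to any of them.

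Section D defines two values per analyte. Baseline is "the average of the three pre-randomization measurements", and the second is "the post-treatment value to be the analyte measurement after 14 days of treatment". The SAP uses the same definitions and reports the same two-level model: "We then used a linear mixed model with random intercepts and main effects for treatment group, the indicator of time (pre- vs. post-treatment". Every listed output is a pre-post quantity: means, change per group, difference in change from water, and the Wald tests. Neither document names a washout value, contrast or summary.

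**The concern.** One of the three study periods produces no planned result. This is not a crossover, so the washout does not separate two treatments, and its only apparent use is to show what happens once exposure stops. Urinary calcium and phosphate are primary outcomes, and the Day 34-35 collection yields samples for them that no planned comparison uses. For a study that calls itself mechanistically informative, whether a change recedes after the inducer or inhibitor is withdrawn is a natural question. Leaving it unplanned also leaves room to choose later among five washout draws. At stake would be a lost finding on reversibility, or a selectively reported one. The primary comparison itself is not in doubt.

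**Working it through.** **1. Samples scheduled against samples used** (Protocol: Baseline, Comparator and Washout Period paragraphs; section D)

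| Period | Blood draws | Urine collections |
|---|---|---|
| Baseline | Days 1, 4, 7 (3) | Days 6-7 (1) |
| Comparator | Days 8, 9, 12, 15, 18, 21 (6) | Days 20-21 (1) |
| Washout | Days 23, 25, 28, 31, 35 (5) | Days 34-35 (1) |
| Total | 14 | 3 |

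If the post-treatment value is Day 21, the analysis uses 4 of 14 blood draws (Days 1, 4, 7, 21) and 2 of 3 urine collections. Over 6 × 20 = 120 participants, the unused washout samples number 5 × 120 = 600 of 14 × 120 = 1,680 draws, and 120 of 3 × 120 = 360 urine collections. Five comparator draws (Days 8, 9, 12, 15, 18) are unused as well, so the plan is an endpoint comparison throughout and does not single out the washout for omission.

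**2. Does Day 21 have to be the post-treatment day?** Rifampin is taken at 8 pm from Day 8, and blood is drawn between 8 am and noon. The Day 21 draw therefore follows 13 doses (Days 8 to 20). The first draw after all 14 is Day 23, which lies in the washout. On that reading one washout draw is used, but Days 25, 28, 31, 35 and the Day 34-35 urine remain unused. There is no recovery contrast on either reading.

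**3. What would an added contrast show?** The documents give no SD, correlation or dropout rate. Assumptions: 20 per arm, complete data, single-measurement variance 1, true changes the same for everyone within an arm. Residual df = 6 × (20 − 1) = 114, so t(0.975) = 1.981 and t(0.80) = 0.845.

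Urine, Day 35 minus baseline, active versus water, independent errors:

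- Variance of one person's change = 1 + 1 = 2, since each time point has one collection.
- SE of the difference between arms = √(2 × 2/20) = 0.447.
- 95% CI half-width = 1.981 × 0.447 = 0.89 SD.
- Difference detected with 80% chance = (1.981 + 0.845) × 0.447 = 1.26 SD.
- A true persisting difference of 1 SD gives 1/0.447 = 2.24 standard errors and a CI excluding zero about 60% of the time. A difference of 0.5 SD does so about 20% of the time.

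If true changes vary between people with variance 1, the variance becomes 3, the half-width 1.981 × √(2 × 3/20) = 1.09 SD and the 80% size 1.55 SD.

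Blood, Day 35 minus the mean of three baseline draws, AR(1) errors with a 3-day correlation of 0 to 0.5: variance 1.333 to 1.609, half-width 0.72 to 0.79 SD, 80% size 1.03 to 1.13 SD.

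**4. Is that the right contrast for receding?** Whether a change has receded is measured by Day 35 minus Day 21, active versus water. Day 35 minus baseline measures what remains. For urine the first has variance 1 + 1 = 2 and the same half-width, 0.89 SD. For blood, Days 21 and 35 are 14 days apart, so the variance is 2(1 − ρ^(14/3)). That is 2 at ρ = 0 and 1.92 at ρ = 0.5, giving half-widths of 0.89 and 0.87 SD. Neither contrast is precise, and a CI including zero would not show full return.

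**5. Two nearby wording points.** The only urine collection before treatment is described by "Urine collection will start on day 6 and continue for 24 hours", so an average of three can exist only for blood. The washout text reads "On day 23, the participants will receive a specimen container for the second 24 hour urine collection", although the Day 20-21 collection is also called the second. The analyst uses the single Day 6-7 collection as the urine baseline and tells the later two apart by their days. Neither point changes a result.

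**The case for a change.** The strongest case for acting is that the samples are already scheduled, the cost is some wording and modest programming, and a separately fitted supportive analysis would leave the primary model untouched. Naming one washout time point in advance would also guard against picking among five. Reversibility bears on a mechanistic study even if it is not a stated objective.

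Much of this stands. The factual gap is real, and the addition would do no harm if reported as estimates with intervals and no significance claims. Three things weaken it as a required change.

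- The stated purpose is the effect of inducing or inhibiting CYP3A4 on biomarkers of calcium homeostasis. The comparison with water at the end of treatment addresses that directly, and unused scheduled samples do not contradict it.
- At the precision shown above, the trial often could not say whether a change had receded or persisted, so the promised gain is smaller than it sounds.
- The documents do not say at which visits the primary analytes were assayed, so the blood part may not be possible. Over the primary outcomes the addition would bring 5 active groups × 2 urine outcomes = 10 supportive estimates, plus 5 × 3 = 15 if blood was assayed at Day 35.

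The SAP is written in the past tense, which suggests that the analysis was already done. Any washout summary would then be supplementary and would lose most of the benefit of being set in advance.

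**Conclusion.** The observation is correct, but it does not call for a change. The Day 34-35 urine and the blood draws from Day 25 on enter no named analysis, nor does Day 23 if the post-treatment value is Day 21. The trial therefore plans no conclusion on recovery. It also states no recovery objective, and the pre-post comparison with water neither needs the washout samples nor is biased by leaving them out.

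A washout contrast would be a secondary description with a 95% CI half-width of roughly 0.7 to 0.9 single-measurement SD, or more if true changes vary between people. Those figures rest on assumed variances and correlations, 20 complete participants per arm, and assay of the analyte at Day 35. Investigators who want to describe the washout data can do so as a labelled supplementary summary. The unnamed post-treatment day, the single urine baseline and the repeated label for the urine collections are matters that an analyst settles from the visit schedule.

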Effect of Modulating CYP3A4 Activity on Mineral Homeostasis

NCT02019875

June 16, 2016

A. PURPOSE OF RESEARCH

Vitamin D is an important regulator of intestinal CYP3A4 (the enzyme responsible for metabolizing a majority of orally administered drugs) and the intestinal calcium transport proteins. Evidence suggests that CYP3A4 activity influences calcium homeostasis by catabolism of the main circulating vitamin D species, 25-hydroxy vitamin D₃ and its active metabolite, 1 α ,25-dihydroxy vitamin D₃. The purpose of this study is to test that hypothesis by evaluating the effect of compounds known to induce (rifampin) or inhibit hepatic (clarithromycin) and/or intestinal (clarithromycin, grapefruit juice) CYP3A4 catalytic activity on biomarkers of calcium homeostasis in healthy adults. This study is not designed to assess the safety or efficacy of the comparator treatments. No conclusions should be drawn in that regard. It is a mechanistically informative clinical study.

B. RESEARCH PROCEDURES INVOLVED

Study Design:

This is an open label, randomized, 3 period protocol to be conducted in healthy adults (18-60 yrs). A targeted enrollment of 120 participants pre-screened for good health will be assigned to one of six comparator groups by randomization. There will be 20 participants in each group. The three sequential study periods will be a 7-day Baseline phase, a 14-day Comparator phase and a 14-day Washout phase. During the Comparator phase of the study, participants will take one of the following by mouth for 14 days based on the group to which they were assigned: 1) 200 mL of water; 2) rifampin 600 mg; 3) 200 mL of grapefruit juice; 4) 200 mL of grapefruit juice plus rifampin 600 mg; 5) clarithromycin 250 mg twice a day and 6) clarithromycin 250 mg twice a day plus rifampin 600 mg once a day.

Study Procedures:

Screening. After providing informed consent, participants will be scheduled for a screening medical history and physical examination at the University of Washington General Clinical Research Center. The participants will also undergo an electrocardiogram (EKG) and screening blood test (metabolic panel). A urine pregnancy test will be performed on all women of child-bearing age. Screening procedures will take approximately one hour. If participants qualify for the study, they will start the baseline period of the study within 2 weeks of the screening visit.

Demographic and Inclusion and Exclusion Criteria.

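### The planned group-by-time model uses baseline only through a change score; it is valid, but baseline adjustment (ANCOVA) would be more precise, mainly for the two urinary primary outcomes

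*Protocol*

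**What the plan says.** Protocol section D sets out the model: "We will use a linear mixed model with random intercepts and main effects for treatment group, the indicator of time (pre- vs. post-treatment", with the group-by-time interaction added. The SAP repeats it in the past tense: "linear mixed model with random intercepts and main effects for treatment group, the indicator of time (pre- vs. post-treatment), and the interaction of the two". In both documents the reported effect is each active group's pre-to-post change minus the change in the water group. Each such difference gets a Wald test, and a global Wald test covers all groups. Baseline is not a covariate, and the group means at baseline are not constrained to be equal.

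On the baseline value, section D says: "We define the baseline value of each analyte to be the average of the three pre-randomization measurements". The Baseline Period paragraph in section B has participants attend "on days 1, 4 and 7 between 8 am - 12 noon for a blood draw", which gives three blood values. For urine it schedules a single collection: "Urine collection will start on day 6 and continue for 24 hours". Section C lists five primary outcomes: PTH, osteocalcin and plasma calcium from blood, and calcium and phosphate from 24-hour urine.

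On size, the Study Design paragraph states: "There will be 20 participants in each group". With six groups the target is 120.

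**The concern.** Baseline is measured before randomisation, so any baseline difference between groups is chance. A model that gives each group its own baseline mean and then takes the difference in change subtracts the whole baseline value, noise included; the slope on baseline is fixed at 1. ANCOVA estimates that slope and subtracts only the part of baseline that predicts the outcome.

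The cost is greatest when baseline is one unaveraged measurement, which is what the visit schedule provides for the two urinary outcomes. With a single baseline and a within-person correlation below 0.5, a change score is noisier than the day-21 value used alone. Each contrast compares only 20 participants with 20, and the documents give no power calculation that would show room to spare.

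**Working it through.** **Inputs from the documents.** Six groups of 20 (6 × 20 = 120). Number of baseline values averaged: k = 3 for blood (days 1, 4, 7) and k = 1 for urine (days 6 to 7). One post-treatment value at day 21, with urine collected over days 20 to 21.

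**Assumptions, because the documents are silent.** Two-sided 5% tests; single-measurement variance 1; complete pairs; the same correlation (ICC) between any two measurements on a person, taken as 0.3, 0.5, 0.7 and 0.9. The plan contains no power or precision figure to reproduce.

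**Step 1: the planned contrast is a change-score contrast.** In one simulated 6 × 20 dataset for each k, the mixed-model interaction and the difference in mean change agreed: -0.1289 (SE 0.3432) by both routes for k = 1, and 0.0280 (SE 0.2695) by both for k = 3.

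**Step 2: variance per participant.**

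- Change score: (1 − ICC)(1 + 1/k)
- ANCOVA: 1 − ICC² / [ICC + (1 − ICC)/k]

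Example, k = 1 and ICC 0.5: change 0.5 × 2 = 1.00; ANCOVA 1 − 0.25/1 = 0.75; SE ratio √(1.00/0.75) = 1.155. With k = 3: change 0.5 × 4/3 = 0.667; ANCOVA 1 − 0.25/0.667 = 0.625; SE ratio 1.033.

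**Step 3: power.** Take the effect that has 80% power under the plan (noncentral t, 114 df). Find its power under ANCOVA with 113 df, after multiplying the ANCOVA variance by 1 + 1/112 for estimating the slope.

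| Baseline | ICC | Change variance | ANCOVA variance | SE ratio | Power with ANCOVA |
|---|---|---|---|---|---|
| One value (urine) | 0.3 | 1.40 | 0.91 | 1.240 | 93% |
| | 0.5 | 1.00 | 0.75 | 1.155 | 90% |
| | 0.7 | 0.60 | 0.51 | 1.085 | 86% |
| | 0.9 | 0.20 | 0.19 | 1.026 | 82% |
| Mean of three (blood) | 0.3 | 0.933 | 0.831 | 1.060 | 84% |
| | 0.5 | 0.667 | 0.625 | 1.033 | 82% |
| | 0.7 | 0.400 | 0.388 | 1.016 | 81% |
| | 0.9 | 0.133 | 0.132 | 1.004 | 80% |

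The SE ratios leave out the slope cost, which lowers each by about half a percentage point. The day-21 value alone has variance 1, so for k = 1 the change score does worse than ignoring baseline whenever 2(1 − ICC) > 1, that is, ICC below 0.5.

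At ICC 0.5 for urine, ANCOVA with 20 per group is worth the planned model with 20 × 1.00/(0.75 × 1.0089) = 26.4 per group.

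**Step 4: simulation.** Over 20,000 null trials per setting, the SE excess was 23%, 14%, 8% and 2% (k = 1) and 5.5%, 2.5%, 1.1% and 0.0% (k = 3). Type I error was 4.6% to 5.3% for both analyses, single and global tests.

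**Step 5: a repair to avoid.** Dropping the treatment main effect while keeping only a random intercept forces equal pre and post variances, which a three-value mean does not satisfy. With k = 3 and 3,000 null trials per setting, single contrasts then rejected in 8.6%, 7.9%, 7.1% and 5.4%, and the global test in 14.1%, 10.9%, 8.3% and 6.3%. With an unstructured 2 × 2 covariance the rates were 4.7%, 5.9%, 5.9% and 5.0%, and 5.9%, 6.3%, 5.6% and 6.0%.

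**The case against.** The best defence is that nothing here is wrong. The planned model is unbiased, and it answers the stated question: change in each group and its difference from water. It also yields pre-treatment means, post-treatment means and within-group changes from a single fit. The gain from ANCOVA rests on a correlation that the documents do not give. It is small for three of the five primary outcomes and, at an ICC of 0.7 to 0.9, modest for urine too. The consistent diet and the creatinine normalisation are meant to reduce within-person noise, though the documents cannot show by how much. The SAP is written in the past tense, so the analysis may be finished.

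Much of this stands: it is a point about efficiency, and the percentages illustrate a range. It does not remove the point. ANCOVA estimates the same treatment contrast, since regressing change on group and baseline gives the same group coefficients as regressing the day-21 value. The within-group summaries can still be tabulated.

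Three technical objections deserve an answer.

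- **Equal correlation.** If the baseline draws correlate 0.7 with each other but 0.5 with day 21, the baseline mean has variance (1 + 1.4)/3 = 0.8. The change variance is 1 + 0.8 − 1 = 0.8, the ANCOVA variance is 1 − 0.25/0.8 = 0.6875, and the blood SE excess is about 8% rather than 3%. That favours ANCOVA further and is still below the 15% for urine.
- **Urine much more stable than blood.** The ranking would reverse only if, for example, the urinary ICC exceeded 0.875 with a blood ICC of 0.5.
- **Reference distribution.** A global Wald test referred to chi-square has a size of about 5.8% here (F with 5 and 114 df). That small excess comes from the reference distribution, not from the change score, and would arise with ANCOVA too.

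**Conclusion.** The concern holds as a matter of precision, not of bias or validity. Validity here means the group contrasts under randomisation with similar change variance across groups. ANCOVA is at least as precise in every case examined, apart from the trivial cost of one slope. The benefit is worth having for urinary calcium and phosphate if they have one baseline collection, as scheduled, and their repeatability is low to moderate. It is small for the blood outcomes under equal correlation. If three baseline urine measurements do exist, the urinary loss falls to the blood figures. The change-score equivalence is exact for complete pairs; with missing values the mixed model also uses partial records.

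The mismatch between the three-measurement baseline in section D and the single urine collection in section B needs no assumption, and it should be settled whichever model is used.

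**What to change.** For each primary outcome, estimate the day-21 differences from water, and the global test, from a model with treatment group and the participant's baseline value as a covariate. Keep the pre- and post-treatment means and the changes as descriptive summaries. If a constrained-baseline mixed model is preferred, specify an unstructured 2 × 2 pre/post covariance; do not simply remove the treatment main effect from the random-intercept model. Add a sentence that defines the urinary baseline separately and agrees with the collection schedule.

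No new data are needed: the cost is one model statement and one sentence. If the analysis is already done, leave the planned result in place and add one table of ANCOVA results, labelled as a sensitivity analysis.

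### Must the plan set an alpha and say whether the global test or the comparisons with water decide each of five primary outcomes?

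*Protocol*

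**What the plan says.** Protocol section C names the primary outcomes as "serum PTH and osteocalcin, plasma calcium concentration and 24-hr urinary calcium and phosphate concentration (normalized for creatinine concentration"). It does not rank them or pick a lead outcome. Section B sets six groups, water and five active, and states: "There will be 20 participants in each group".

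Section D fits one mixed model per analyte. From it the analysts take the group means before and after treatment, the change in each group, and "the difference in change in analyte comparing each active treatment group with the change observed in the water group". On testing, section D says: "We will use a Wald test to test each difference in change compared with water, and a global Wald test". Each of those five differences thus gets its own Wald test, and there is also one global test per analyte.

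The SAP repeats this. Its comparisons read: "We used a Wald test to test each difference in change compared with water". Its global test is "a global Wald test to test the null hypothesis that all pre- vs post-treatment changes were the same across treatment group". Neither document states a significance level, sidedness, an adjustment, an order of testing, or which result carries the conclusion for an outcome.

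On purpose, section A says: "This study is not designed to assess the safety or efficacy of the comparator treatments". It presents the study as mechanistic, but it also says that the aim is to test a hypothesis, and it does not call the analysis exploratory.

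**The concern.** The outcomes are labelled primary and formal tests are planned, so a reader expects to know the level of each test and which one settles the matter. Here there are 30 tests on primary outcomes and no such statement. Both kinds of test use the same data. One active group can differ from water at p<0.05 while the global test for that outcome is not significant. An analyst could then report either that the outcome changed or that it did not, and could choose after seeing the results.

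With 25 unadjusted comparisons, some will cross 0.05 by chance. If the report does not say whether a p-value is confirmatory or descriptive, one isolated hit could be taken as proof that changing CYP3A4 activity alters calcium balance.

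**Working it through.** **Inputs from the documents.** Five primary outcomes (section C); six groups of 20, so 6 × 20 = 120 (section B); five comparisons with water and one global test per analyte (section D and SAP). The documents give no alpha, power, effect size or SD, so there is no stated error rate to reproduce.

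**Assumptions.** Two-sided 0.05, all 20 per group retained, common variance, equal correlation between outcomes of 0 to 0.7. Effects are in SD of the change.

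**Number of tests.** 5 × 5 = 25 comparisons, plus 5 global tests, makes 30. Any vitamin D species analysed the same way would add more.

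**One outcome, no effects.** Simulation with a shared water group and 114 degrees of freedom (critical t 1.981, critical F 2.294):

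- At least one comparison significant: 0.181. Five independent tests would give 1 − 0.95^5 = 0.226; the shared control lowers it.
- At least one comparison significant, global test not: 0.141, which is 0.141 / 0.181 = 78% of the outcomes with any hit.
- Global test significant, no comparison significant: about 0.009 to 0.010.

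**Five outcomes, no effects.** At correlation 0, the chance of any false-positive comparison is 1 − (1 − 0.181)^5 = 0.63; at correlation 0.7 the simulation gives 0.46. For a hit without its global test, 1 − (1 − 0.141)^5 = 0.53 at correlation 0, and about 0.42 at 0.7.

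**Three rifampin groups change all five outcomes.** The direction at issue is a significant comparison without a significant global test. The reverse is a different matter, because active groups can differ from one another without any one differing clearly from water.

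| Effect (SD of change) | Power of one comparison | Hit without global test, on at least one of five outcomes |
|---|---|---|
| 1.03 | 90% | about 1% |
| 0.89 | 80% | about 5 to 7% |
| 0.63 | 50% | about 35 to 45% |

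For the first row, the rate per outcome is 0.002, so 1 − 0.998^5 = 0.010. The reverse pattern runs at 0.008 per outcome. Pooling the two gives 1 − 0.990^5 = 0.049, most of which is the reverse pattern.

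At 1.03 SD, the chance of a false positive among the two groups without rifampin is 26 to 38%. Requiring a significant global test first could remove at most the roughly 1% of trials in which a hit lacks one, so this figure would hardly move.

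**Price of a rule.** Power of one comparison is Φ(d√(n/2) − z), with n = 20 and d = 0.886, so d√(n/2) = 2.802:

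- Unadjusted 0.05: Φ(2.802 − 1.960) = 0.80.
- Bonferroni within an outcome, 0.05 / 5 = 0.01: Φ(2.802 − 2.576) = 0.59.
- Bonferroni over all comparisons, 0.05 / 25 = 0.002: Φ(2.802 − 3.090) = 0.39.

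Requiring the global test at 0.05 is cheaper. A comparison with 90% power keeps 0.901 × (1 − 0.052) = 0.854 if only that group is active, and 0.901 × 0.999 = 0.900 if all three rifampin groups share the effect.

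**Consistency as evidence.** With no effects, all three rifampin groups are significant in the same direction on some outcome in only 1.3 to 1.7% of trials. An isolated hit is common by chance; a consistent rifampin pattern is not.

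**The case for a change.** The strongest case for a change is that the remedy costs almost nothing. Stating alpha, saying whether the global test decides or supports, and labelling the p-values needs no new data and loses no power. The mechanistic aim does not remove the need, since the protocol sets out to test a hypothesis on outcomes it calls primary. Nor do the documents give a power basis for assuming effects large enough to make the two tests agree; at 0.63 SD the mismatch is frequent.

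Much of this stands. The silence is real, the false-positive rates hold under the stated assumptions, and an isolated hit should not be read as confirmation. What does not stand is the claim of two opposite readings. The global test asks whether all six groups changed alike; each comparison asks whether one group's change differs from water's. Failing to reject with 5 degrees of freedom does not show that no group changed, so it cannot overturn a single comparison. Neither document makes the global test a condition for anything. The 78% figure comes from the complete-null case and reflects setting a six-group F test beside comparisons with a control, rather than a fault specific to this plan.

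**Conclusion.** No change to the plan follows. What is missing is a sentence on interpretation, and either choice of role for the global test would leave every estimate, the model and all 30 planned tests as they are. The plan already fixes which contrasts are drawn and tested, and an analyst would sensibly use two-sided 0.05, present both kinds of test and treat the p-values as unadjusted. With all 25 comparisons shown, a reader could apply a stricter threshold.

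Formal adjustment is a trade-off on which reasonable statisticians would differ. It would take a comparison from 80% power to 59% or 39%. Using the global test as a first step would help mainly when nothing works: false positives across five outcomes then fall from about 63% to about 18% at correlation 0. It would barely help if rifampin acts throughout.

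The point to carry forward is one of reading. One or two nominally significant comparisons among 25 are weak evidence; agreement across the three rifampin groups is much stronger. All rates rest on an assumed two-sided 0.05, full retention, common variance, and assumed correlations and effect sizes, none of which the documents give.
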